5.3 Pretreatment Criteria

The first dose of Everolimus may be administered on the same day as enrollment but no more than 10 business days after enrollment. The treatment period begins on the first day of treatment with Everolimus.

If a subject is unable to come into the clinic for a required study visit or if unforeseen events occur, the visit procedures may be performed within a one week time frame.

The following assessments will be performed at each clinic visit according to table 3.4 throughout the treatment period:

- Physical examination,
- ECOG performance status,
- Blood pressure, respiratory rate, resting pulse, temperature, and weight.
- Laboratory evaluations: If patients have met trial eligibility within the previous 72 hours, no specific criteria will need required in order to initiate the protocol unless, in the investigator's opinion, significant medical issues arise which would contraindicate starting the study medications. If patients have completed entry criteria >72 hours prior to cycle 1 day 1, laboratory values on cycle 1 day 1 should be repeated to confirm all eligibility criteria are met.
- CT scans (contrast-enhanced) or MRI scan (contrast-enhanced) or PET-CT scan of areas of known disease every 8 weeks with a 5 business-day time window in case unforeseen events occur. Evaluation according to RECIST criteria compared to previous scan.
- beta HCG pregnancy test for women of child-bearing potential

Documentation of all adverse events will occur at each clinic visit and at any other time point when necessary. There are no specific criteria for the initiation of a given cycle except for the ones indicated in the dose modification tables 6-2, 6-3 & 6-4. Study subjects may commence with treatment if, in the opinion of the investigator and based on the guidance of Section 6, it is safe for the participant to do so.

5.4 Agent Administration

Everolimus will be administered orally daily, either at the starting dose of 10 mg, or at a lower dose based on guidance in Section 6.

5.5 General Concomitant Medication and Supportive Care Guidelines

Any new medications that patients might start taking while on study need to be reported to the study MD first before they start taking it. At each visit, the investigator will ask the patient about any new medications he/she is or has taken after the start of the study drug.

All Concomitant medications/Significant non-drug therapies taken ≤ 30 days prior to start and after start of study drug, including physical therapy and blood transfusions, should be recorded.

The following restrictions apply during the entire duration of the study:

- No other investigational therapy should be given to patients.
- No anticancer agents other than the study medication should be given to patients. The only exception is that treatment with hormonal agents for either prostate or breast cancer may be continued (not added) during this study. If such agents are required for a patient then the patient must first be withdrawn from the study.
- Growth factors (e.g. G-CSF, GM-CSF, erythropoietin, platelets growth factors etc.) are not to be administered prophylactically but may be prescribed by the investigator for rescue from severe hematologic events, if this is thought to be appropriate.
- Concurrent administration of Everolimus and strong CYP3A4 inhibitors (such as ketoconazole, itraconazole, ritonavir) and inducers (such as rifampin, rifabutin) should be avoided. Provided there is no alternative treatment available, patients should be closely monitored for potential toxicities.
- Concurrent administration of Everolimus and moderate CYP3A4 inhibitors (such as erythromycin, fluconazole, calcium channel blockers, benzodiazepines) and moderate CYP3A4 inducers (e.g. carbamazepine, phenobarbital, phenytoin) should also be avoided if possible, or used subject to caution (e.g. increased frequency of safety monitoring, temporary interruption of Everolimus).
- Competitive inhibition could occur when Everolimus is combined with drugs which are also CYP3A4 substrates. Therefore caution should be exercised in such cases.
- Co-administration with substrates, inducers, or inhibitors of P-glycoprotein should be avoided, if possible, or used subject to caution (e.g. increased frequency of safety monitoring, temporary interruption of Everolimus).
- Grapefruit and grapefruit juice affect cytochrome P450 and P-glycoprotein activity and should therefore be avoided.
- In addition, patients should avoid Seville oranges and star fruit, as well as the juice of these fruits, which are potent CYP3A4-inhibitors.
- No chronic treatment with systemic steroids or another immunosuppressive agents. Topical or inhaled corticosteroids are allowed.
- Everolimus may affect the response to vaccinations making the response to the vaccination less effective. Live vaccines should be avoided while a patient is treated with Everolimus.

Oral anticoagulants such as warfarin are CYP2C9 substrates and, as such, no interaction with Everolimus is expected. However, drug-drug interaction studies between macrolide antibiotics and warfarin have produced mixed outcomes and the disparity in these findings has led to the conclusion that multiple factors may alter the clearance of warfarin. The co-administration of Everolimus and oral anticoagulants is possible but should be subject to verification of coagulation (INR) once steady state is reached (after one week's treatment).

A comprehensive list of cytochrome P450 isoenzymes and CYP3A4 inhibitors, inducers, and substrates can be found at <http://medicine.iupui.edu/flockhart>. This website is continually revised and should be checked frequently for updates.

Please refer to Table 5-1 listing relevant inducers and inhibitors of CYP3A and Table 5.2 for a list of relevant substrates, inducers, and inhibitors of PgP.

Table 5-1 clinically relevant drug interactions: inducers, and inhibitors of isoenzyme CYP3A

Inducers
carbamazepine, glucocorticoids, modafinil, oxcarbazepine, phenobarbital, phenytoin, pioglitazone, rifabutin, rifampin, St. John's wort, troglitazone, efavirenz, nevirapine, topiramate, avasimibe, bosentan, etravirine, nafcillin, ritonavir, talviraline (not available in US market), tipranavir, amprenavir, aprepitant, armodafinil (R-modafinil), dexamethasone, nevirapine, prednisone, pleconaril (not available in US market), rufinamide
Inhibitors
Strong inhibitors: clarithromycin, conivaptan, indinavir, itraconazole, ketoconazole, lopinavir, mibefradil, nefazodone, nelfinavir, ritonavir, saquinavir, telithromycin, troleandomycin, voriconazole, tipranavir, elvitegravir, Posaconazole (Krishna et al 2009)
Moderate inhibitors: aprepitant, atazanavir, casopitant, cimetidine, ciprofloxacin, darunavir, diltiazem, erythromycin, fluconazole, grapefruit juice (citrus parasidi fruit juice), imatinib, tofisopam, verapamil, amprenavir, fosamprenavir, dronedarone

Table 5-2 Clinically relevant drug interactions: substrates, inducers, inhibitors of Pgp and Pgp/CYP3A dual inhibitors

Substrates
digoxin, fexofenadine, indinavir, vincristine, colchicine, topotecan, paclitaxel
Inducers
rifampin, St John's wort
Pgp Inhibitors and Pgp/CYP3A Dual Inhibitors
amiodarone, captopril, carvedilol, clarithromycin, conivaptan, diltiazem, dronedarone, elacridar, erythromycin, felodipine, fexofenadine, ginkgo (ginkgo biloba), indinavir, itraconazole, lopinavir, mibefradil, milk thistle (silybum marianum), nifedipine, nitrendipine, quercetin, quinidine, ranolazine, ritonavir, saquinavir, Schisandra chinensis, St John's wort (hypericum perforatum), talinolol, telmisartan, tipranavir, valsopodar, verapamil
Reference: Internal Clinical Pharmacology Drug-drug interaction (DDI) memo, updated Oct. 2, 2011, which summarizes DDI data from three sources including the FDA's "Guidance for Industry, Drug Interaction Studies", the University of Washington's Drug Interaction Database, and Indiana University School of Medicine's Drug Interaction Table.

Vaccinations

Immunosuppressants may affect the response to vaccination and vaccination during treatment with Everolimus may therefore be less effective. The use of live vaccines should be avoided during treatment with Everolimus. Examples of live vaccines are: intranasal influenza, measles, mumps, rubella, oral polio, BCG, yellow fever, varicella, and TY21a typhoid vaccines.

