3.1 Eligibility Criteria

Participants must meet the following criteria on screening examination to be eligible to participate in the study:

- 3.1.1 Participants must have histologically confirmed advanced malignancy that is metastatic and/or unresectable and/or recurrent with confirmed inactivating mutations in TSC1 or TSC2 or activating MTOR mutations, identified in any

CLIA-certified laboratory. All genetic findings must be reviewed by the study PI, [name], prior to study entry.

Biopsy of a primary or metastatic lesion must have been performed within the past two years. Sufficient pathologic material must be available to enable whole exome sequencing at the time of study entry. Patients with biopsy samples older than 2 years must undergo a fresh tumor biopsy or should receive approval for enrollment from the Principal investigator.

- 3.1.2 Participants must have measurable disease, defined as at least one lesion that can be accurately measured in at least one dimension (longest diameter to be recorded for non-nodal lesions and short axis for nodal lesions) as ≥ 20 mm with conventional techniques or as ≥ 10 mm with spiral CT scan, MRI, or calipers by clinical exam. See Section 10 for the evaluation of measurable disease.
- 3.1.3 Participants may have received any number of prior therapies, from 0 to > 10 . Prior treatment with PI3-kinase or mTOR inhibitors is not permitted, unless they were given as adjuvant therapy without undue toxicity, and without suggestion of resistance to therapy.
- 3.1.4 Age ≥ 18 years.
- 3.1.5 ECOG performance status ≤ 2 (see Appendix A).
- 3.1.6 Participants must have normal organ and marrow function as defined below:
- Leukocytes $\geq 3,000/\text{mcL}$
 - Absolute neutrophil count $\geq 1,500/\text{mcL}$
 - Platelets $\geq 100,000/\text{mcL}$
 - Hemoglobin ≥ 9.0 gr/dL
 - total bilirubin ≤ 1.5 X the institutional upper limit of normal (ULN)
 - AST (SGOT)/ALT (SGPT) ≤ 2.5 X institutional upper limit of normal.
Patients with confirmed liver metastases are permitted to have AST/ALT at levels ≤ 5 X the institutional upper limit of normal (ULN)
 - creatinine ≤ 1.5 X the institutional upper limit of normal (ULN)
 - Total cholesterol < 300 mg/dL
 - Triglycerides < 250 mg/dL

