3.2 Exclusion Criteria

Participants who exhibit any of the following conditions at screening will not be eligible for admission into the study.

- 3.2.1 Participants who have had any of the following:
 - 3.2.1.1 Chemotherapy in the previous 2 weeks (6 weeks for nitrosoureas or mitomycin C)
 - 3.2.1.2 Radiotherapy within 3 weeks
 - 3.2.1.3 Investigational agents within 3 weeks prior to entering the study
 - 3.2.1.4 Patients who have not recovered from significant (in the opinion of the investigator) adverse events due to previous agents administered.
- 3.2.2 Child-Pugh B or C hepatic impairment. Patients with a history of hepatitis or significant exposure risk should be tested for hepatitis B and C with serologic markers: HBsAg, HBs Ab, HBcoreIgG Ab, and HCV Ab. Patients with active hepatitis B or C are excluded.
- 3.2.3 Participants may not be receiving any other research study agents.
- 3.2.4 Uncontrolled brain or leptomeningeal metastases, including patients who continue to require glucocorticoids for brain or leptomeningeal metastases. Asymptomatic or treated brain metastases are acceptable.
- 3.2.5 History of allergic reactions attributed to compounds of similar chemical or biologic composition to everolimus.
- 3.2.6 A list of prohibited medications on study are listed in Section 5.5
- 3.2.7 Chronic treatment with corticosteroids or other immunosuppressive therapy

13-March-2017

- 3.2.8 Uncontrolled intercurrent illness including, but not limited to ongoing or active infection, symptomatic congestive heart failure, unstable angina pectoris, cardiac arrhythmia, or psychiatric illness/social situations that would limit compliance with study requirements.
- 3.2.9 Pregnant women are excluded from this study because everolimus has the potential for teratogenic or abortifacient effects. Because there is an unknown but potential risk of adverse events in nursing infants secondary to treatment of the mother with everolimus, breastfeeding should be discontinued if the mother is treated with everolimus. These potential risks may also apply to other agents used in this study.

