5.2 Screening Criteria

All subjects or their legally acceptable representative and the person who conducted the informed consent discussion must personally sign and date the consent form before any study-specific screening procedures are performed. Procedures that have been performed before consent was obtained as part of routine care are not considered study-specific procedures.

Medical history information to be collected during screening must date back to the original diagnosis of cancer. If a subject is referred to the study center, a copy of all applicable reports and histological or cytological evidence, confirming the diagnosis must be provided to the study center before enrollment. Copies of recent (i.e., within the past 6 months) radiographic images confirming disease progression by modified RECIST should be provided to the study center.

All subjects who have signed the IRB approved consent form must be registered as a screened subject. At the time of registration, the subject will receive a unique 2 digit subject identification number. This number will be used to identify the subject throughout the study and must be used on all study documentation related to that subject. The subject identification number must remain constant throughout the entire study.

All screening tests and procedures must be performed and the results available within a maximum of 14 days before study day 1 unless otherwise noted.

Subjects who do not meet eligibility criteria within the 14 day screening period will not be eligible for enrollment. However, subjects may be re-screened up to 2 additional times at the discretion of the investigator. The subject must be re-consented if more than 28 days have elapsed since the date of last informed consent.

The following screening assessments must be performed:

- Review of inclusion and exclusion criteria
- Medical history review, documentation of diagnosis and previous treatment.
- Physical examination, ECOG performance status, blood pressure, respiratory rate, resting pulse, temperature, height and weight.
- CT scans (contrast-enhanced) or MRI scan (contrast-enhanced) of areas of known disease and that are of acceptable quality as baseline study within 30 days prior to study day 1.

Laboratory assessment consisting of

- Hematology
- Chemistry
- Urinalysis
- beta HCG pregnancy test for women of child-bearing potential

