14.1 Study Design/Endpoints

The primary objective of this trial is objective response rate according to RECIST 1.1 criteria.

Secondary objectives include duration of response, progression-free and overall survival. Duration of response is defined as the time from RECIST-confirmed response (CR+PR) to documented disease progression. Progression-free survival is defined as the time from study registration to documented disease progression per RECIST 1.1 or death from any cause, whichever occurs first. Patients not experiencing a PFS event will be censored at the date of their last disease assessment. Overall survival is defined as time from registration to death from any cause, censoring patients thought to be alive at the time of final analysis at the last date of follow up. We will also estimate toxicity via CTCAE version 4.0, and the association of IHC and whole exome sequencing results with patient outcomes and other genetic events.

We will estimate event-time distributions using the Kaplan-Meier method, using Greenwood's formula to estimate the variance and provide 90% confidence intervals for the medians, 6-month, and 1-year estimates. Categorical outcomes, such as toxicity and response, will be estimated and their corresponding 90% exact binomial confidence intervals will be provided.

For the cohort of patients with TSC1 and TSC2 mutations, we will conduct this study using a Simon's two-stage design. In the first stage we will enroll 21 patients and if a total of at least 4 responses (CR + PR) are observed among them, accrual to the second stage will open. If 3 or fewer responses are observed among the first 21 patients, the study will terminate. In the second stage, an additional 29 patients will be enrolled for a total study accrual of 50 patients. After accrual to the second stage is completed, we will declare study success if at least 8 responses are observed among the 50 registered patients. This design has a probability of stopping early after the first stage of accrual of 85% if the drug is ineffective; the overall power of the study to detect the targeted response rate of 30% (compared to a null of 10%) is 91% while controlling the type I error at a one-sided level of 0.07.

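### Section 5.5 lets hormonal agents for breast or prostate cancer continue, and nothing keeps a response to a recently started one from being counted as an everolimus response

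*Combined protocol and SAP*

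**What the plan says.** Section 5.5 bars anticancer agents other than study drug, then makes one allowance: "The only exception is that treatment with hormonal agents for either prostate or breast cancer may be continued (not added) during this study". The next sentence reads "If such agents are required for a patient then the patient must first be withdrawn from the study".

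The entry criteria set no condition on the continued agent:

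- Section 3.1.1 asks for "histologically confirmed advanced malignancy that is metastatic and/or unresectable and/or recurrent". Progression is not named.
- Section 3.1.3 says "Participants may have received any number of prior therapies, from 0 to > 10".
- The washouts in Section 3.2.1 begin with "Chemotherapy in the previous 2 weeks (6 weeks for nitrosoureas or mitomycin C" and go on to radiotherapy and investigational agents. Hormonal therapy is not among them.

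Section 5.2 says of scans from the past six months that "radiographic images confirming disease progression by modified RECIST should be provided to the study center". It does not say on which treatment, if any, the progression occurred.

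On the endpoint, Section 14.1 states "The primary objective of this trial is objective response rate according to RECIST 1.1 criteria" and, for the TSC1/TSC2 cohort, "we will declare study success if at least 8 responses are observed among the 50 registered patients". Section 10.1.4.3 takes the best response from the start of treatment. Neither section has a rule or a sensitivity analysis for patients on continued hormonal therapy.

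**The concern.** The protocol itself classes these hormonal agents as anticancer treatment, since the permission is an exception to the ban on such treatment. Section 2.1.1 describes the breast cancer approval of everolimus as a combination with a hormonal agent after earlier hormonal agents had failed, so a response on both drugs is not evidence about everolimus alone.

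A patient who started a hormonal agent a few weeks before entry meets every numbered criterion. If the tumour then shrinks past 30% from baseline, the patient is a responder, and no control arm separates the two drugs. The 10% null rate and the 0.07 error rate in Section 14.1 presuppose that no response comes from the other treatment. The success thresholds are low counts: 4 in 21, 8 in 50, and 2 in 10 for the MTOR cohort. A single misattributed response therefore carries weight.

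**Working it through.** **Inputs from Section 14.1:** stage 1 n = 21, continue with at least 4 responses; total N = 50, success with at least 8; null 10%, target 30%; stated early stopping 85%, power 91%, one-sided type I error 0.07.

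**1. Reproduce the plan.**
P(success | p) = Σ over x = 4 to 21 of P(X₁ = x | 21, p) × P(X₂ ≥ 8 − x | 29, p).

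- Early stopping at p = 0.10: P(X₁ ≤ 3) = 0.848.
- Type I error at p = 0.10: 0.0662.
- Power at p = 0.30: 0.912.

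These agree with the stated figures, so the design arithmetic is sound.

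**2. Unconditional effect of a few hormone-continuing patients.** The documents give neither their share s nor their hormonal response probability h, so both are assumptions. Take h from 20% to 40%, independent of a 10% null response to everolimus. Such a patient responds with probability q = 1 − 0.9(1 − h), that is 0.28 at h = 20% and 0.46 at h = 40%. The average response rate becomes p = (1 − s)(0.10) + s·q, which goes into the formula above.

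| Such patients in 50 | p at h = 20% | Type I error | p at h = 40% | Type I error |
|---|---|---|---|---|
| 0 | 0.1000 | 0.066 | 0.1000 | 0.066 |
| 1 | 0.1036 | 0.077 | 0.1072 | 0.090 |
| 2 | 0.1072 | 0.090 | 0.1144 | 0.117 |
| 5 | 0.1180 | 0.132 | 0.1360 | 0.220 |

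The row for 5 only shows the direction; nothing in the documents supports that share.

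**3. Conditional effect: a misattributed response has already occurred in stage 1.** With k such responses and the other 21 − k stage 1 patients at 10%:

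| k | P(stop early) | P(success) |
|---|---|---|
| 0 | 0.848 | 0.066 |
| 1 | 0.677 | 0.150 |
| 2 | 0.420 | 0.293 |

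For the MTOR cohort (at least 2 of 10), P = 0.264 with none. With one already present, the other nine need only one more: 1 − 0.9⁹ = 0.613.

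**4. Does Section 5.2 close the gap?** No. Progression within six months can predate the start of the hormonal agent, the sentence ties it to no treatment, and it stands outside the numbered criteria.

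**The case against.** **Exposure may be very small.** The tumour types named in Sections 14 and 14.2 are bladder, pancreatic neuroendocrine, PEComa, squamous lung and anaplastic thyroid; neither breast nor prostate appears. A patient also needs a qualifying mutation, measurable disease, and an agent started recently enough to produce new shrinkage after baseline. This stands, and it is why the unconditional figures for 1 or 2 patients are the fair measure of size. It does not remove the point, because Section 5.5 names both cancers and so expects them.

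**There are partial safeguards.** Response is measured from a scan within about four weeks of day 1, so earlier hormonal shrinkage is not credited. Section 5.5 has medications from the previous 30 days recorded, and Appendix C (3.7.2) has outside sites send a clinician-reviewed medication list before registration. This also stands. It limits the bias to shrinkage after baseline and makes the patients identifiable, but no analysis uses the record.

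**A reader might infer that Sections 3.1.3 and 5.2 contradict each other and let sites enrol different populations.** The documents do not support that. Section 3.1.3 concerns the number of prior therapies and is silent on progression. Section 5.2 is a documentation step worded as a recommendation, and it does not speak of progression on treatment, so an untreated patient with recurrent disease could satisfy it. Section 4.2 makes the inclusion and exclusion criteria govern registration. The two sections are unreconciled: an untreated, newly metastatic patient with no earlier imaging meets 3.1 but cannot supply the scans that 5.2 asks for.

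**A reader might also take the rise from 6.6% to 15% or 29% as the design's inflated error rate.** It is not. Those values assume that one or two misattributed responses have already happened in stage 1. The MTOR figure is conditional in the same way, and Section 14.1 already calls inference in that cohort limited.

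**Conclusion.** The gap is real and narrow. The plan permits a concurrent anticancer treatment, sets no condition on progression under it, and counts every response alike. Following the plan as written can therefore credit everolimus with a hormonal response. That this will happen is not shown.

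With 1 or 2 such patients in 50, type I error is about 0.08 to 0.12 against 0.066. This rests on the assumed 20% to 40% hormonal response rate, on independence of the two effects, and on these being patients whose hormonal agent can still produce a new response. For a patient already progressing on the agent, the 20% to 40% rate would not be a reasonable assumption. The figures also take the 21+29 rule as operative; Sections 3 and 14.3 give a total of 30 patients, which is a separate matter to settle.

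The change is worth making because it is cheap and the thresholds are small counts.

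**What to change.** 1. **Sections 3.1 and 5.5.** State in 3.1, with a cross-reference in 5.5, that a patient entering on a continuing hormonal agent counts toward the primary endpoint only if objective progression on that agent was documented before the baseline scan. Say whether other such patients are ineligible or are enrolled but not counted. If the latter, say that they leave both numerator and denominator and whether they are replaced, so that the 21 and 50 keep their meaning.
2. **Section 14.1.** Prespecify the response rate with and without all patients on continued hormonal therapy, using the concomitant medication record already collected. Make sure that the record includes the agent's start date. This step excludes nobody and is worth doing even if step 1 is declined.
3. **Section 5.5.** Reconcile the exception with the sentence after it on withdrawal. As placed, the scope of that sentence is unclear: it can be read as covering the agents that the exception allows.
4. **Section 5.2.** Reconcile the request for progression images with 3.1, and replace modified RECIST, which is nowhere defined, with RECIST 1.1 as used in Section 10.

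The cost is a few sentences in an amendment and one line on the eligibility checklist. The downside is small: a few breast or prostate patients without documented progression on their hormonal agent become ineligible or are not counted.
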